2. INTRODUCTION

Bermekimab (also known as JNJ-77474462 and MABp1) is a recombinant human immunoglobulin G1 kappa (IgG1κ) monoclonal antibody (mAb) specific for human interleukin-1 alpha (IL-1α). Interleukin-1 alpha is a key mediator of cutaneous inflammation and is constitutively and inducibly expressed by several cell types, including keratinocytes where high levels of IL-1α are present in healthy individuals, these data suggest that IL-1α has the potential to mediate inflammation in the skin.

Bermekimab has been investigated in dermatologic clinical studies and other indications. Two Phase 2 studies are currently ongoing: one in atopic dermatitis (AD; Study 2018-PT044 [[NCT03496974](#)]) and one in hidradenitis suppurativa (HS; Study 2018-PT045). Bermekimab has been administered intravenously (IV) at doses ranging from 0.25 mg/kg to 7.5 mg/kg and subcutaneously (SC) at doses ranging from 100 mg to 800 mg.

For the most comprehensive nonclinical and clinical information regarding bermekimab, refer to the latest version of the [Investigator's Brochure](#) (IB) and Addenda for Bermekimab.

The term “study intervention” throughout the protocol, refers to study drug as defined in Section [6.1](#). Study Intervention Administered. For the purpose of this study protocol, the study intervention will be referred to as ‘bermekimab’.

The term “sponsor” used throughout this document refers to the entities listed in the Contact Information page(s), which will be provided as a separate document.

The term “participant” throughout the protocol refers to the common term “subject”.

2.1. Study Rationale

Atopic dermatitis (AD) is a chronic/relapsing inflammatory skin disease characterized by intense pruritus (ie, itchiness), xerosis (skin dryness), and eczematous lesions whose features include erythema, infiltration/papulation, oozing with crusting, excoriations, and lichenification. It is often associated with other atopic disorders, such as allergic rhinitis and asthma. Severe disease can be extremely disabling due to several factors: major psychological problems, significant sleep loss, and impaired quality of life (QoL) that lead to a high socioeconomic cost. An estimated 2% to 10% of adults are affected by AD ([Bieber 2008](#)).

Inhibition of IL-1α has been shown clinically to resolve chronic skin inflammation. However, it is not fully known what levels of IL-1α are present in active skin lesions from patients with AD and what dose level of bermekimab would maximally neutralize IL-1α in active lesions. Evaluating this question in the context of clinical response would improve our understanding of the role of IL-1α in AD disease pathophysiology.

Efficacy results from 2 open label studies (2018 PT-044 and PT-045), and preliminary results from an ongoing randomized phase 2 trial (77474462ADM2002, [NCT04021862](#)) of bermekimab SC 400 mg weekly show a dose-response relationship. However, the data suggests additional room for improvement in efficacy outcomes.

Given the favorable safety profile observed to date in multiple trials including at the highest dose (1200 mg IV) in a single dose evaluation, this study has been designed to evaluate the efficacy of

higher doses of bermekimab, which need to be administered as weekly in IV infusions, coupled with detailed tissue evaluations. The purpose is to provide a comprehensive analysis of safety, pharmacokinetics (PK), pharmacodynamics (PD), including target engagement, and efficacy, in patients with moderate-to-severe AD, to understand the full potential of IL-1 α inhibition in AD.

In summary, this is a Phase 2a, randomized, adaptive, placebo-controlled, double-blind, multicenter, interventional study to assess the safety, efficacy, PK, and immunogenicity of multiple IV doses of bermekimab in adult participants with moderate-to-severe AD using a placebo control by means of:

- Assessment of the efficacy of multiple IV infusions of bermekimab through Week 16
- Evaluating safety and tolerability data for bermekimab in these participants with AD.

The scientific rationale in support of the study as well as relevant background information pertaining to nonclinical and clinical studies of bermekimab are summarized in Section 2.2. Background.

An overview of the protocol design, supportive rationale, and justification for dose are described in Sections 4.1 (Overall Design), 4.2 (Scientific Rationale for Study Design), and 4.3 (Justification for Dose), respectively.

2.2. Background

Interleukin-1 α plays a key role in the pathophysiology of a wide range of inflammatory skin disorders (Bou-Dargham 2017). Keratinocytes are a major reservoir of IL-1 α and may be a key source of inflammatory stimulus in AD. Skin barrier defect and dysbiosis in AD stimulates keratinocytes to secrete chemokines and innate cytokines such as IL-1 α , resulting in leukocyte infiltration and trafficking into skin to sustain chronic inflammation in AD. Interlukin-1 α is a key inducer of matrix metalloproteinases activity which could be directly involved in the epithelial barrier breakdown in AD (Han 2005).

In addition to being a driver of inflammation, IL-1 α has been shown to induce pain mediator substance P secretion by neurons (Skoff 2009). Neutralizing IL-1 α activity resolved chronic skin inflammation in the study by Skoff and strongly supported IL-1 α as a key target for treating AD, along with other inflammatory skin diseases.

Clinical evidence generated to date suggests that targeting IL-1 α maybe an effective treatment in undermining the inflammatory process that drives a wide array of diseases, including dermatologic conditions.

In previous dermatology studies, bermekimab demonstrated therapeutic activity and a well--tolerated safety profile.

Nonclinical Studies

This section provides a summary of the sponsor's assessment of how the overall nonclinical data support the safety of the proposed dosing for bermekimab in this Phase 2 program in AD.

A comprehensive overview of the nonclinical development program for bermekimab is available in Section 3 of the latest version of the bermekimab [IB](#).

Nonclinical Pharmacology

Bermekimab binds with high affinity and specificity to human IL-1 α with a dissociation rate constant (K_D) of 0.029 nM. No binding to human IL-1 β or interleukin-1 receptor antagonist (IL-1Ra) was detected up to the highest concentrations tested. In addition, bermekimab was shown to effectively neutralize the ability of human IL-1 α to induce endothelial cell expression of adhesion molecules and fibroblast expression of interleukin-6 (IL-6). Bermekimab was bound by cynomolgus monkey IL-1 α with a K_D of 1.3 nM and did not bind with mouse, rat, or pig IL-1 α at the highest concentrations tested.

Toxicology

A 1-month single- and repeat-intraperitoneal (IP) dose mouse study tested JNJ-77474462 up to 3 doses of 312 mg/kg/week. There were no treatment-related deaths following the single- or short-term repeat-dose administration. There were no treatment effects on clinical observation, body weight, food consumption, body temperature, clinical pathology, and histopathology evaluations. Mice that received a single high dose or 2 intermediate doses had minimal, but statistically significant decreases in blood urea nitrogen (BUN) which were attributed to intergroup variation since no similar decrease was observed in the mice that received 3 high doses. Slight increases in total protein and globulin seen in the high dose animals were likely due to the administration of the protein test article.

The potential toxicity of bermekimab was evaluated in a 6-week repeat IV and SC exploratory and tolerability study with toxicokinetics in female cynomolgus monkey, at dose levels of 0, 50 (IV), 300 (IV), and 300 (SC) mg/kg/week for 6 weeks. The toxicology evaluations included mortality, clinical observation, body weight, food consumption, veterinary physical examination, ophthalmology, clinical pathology (hematology, chemistry, coagulation, and urinalysis), organ weight, gross necropsy, and histopathology. In addition, safety pharmacology and physiology endpoints (electrocardiogram, blood pressure, heart rate, respiratory rate, and body temperature) were evaluated. There was a transient decrease in blood pressure only at the high dose for both IV and SC administrations on Day 6 and the values returned to baseline at the end of dosing period (Day 37). There were no other treatment-related findings at any dose levels. The no observed adverse effect level (NOAEL) was 300 mg/kg for both IV and SC administrations. At the NOAEL dose, the exposures maximum serum concentration (C_{max}) and area under the curve (AUC) for IV administration were 9048.26 μ g/mL and 26032.83 μ g·day/mL respectively and C_{max} and AUC for SC administration were 4482.98 μ g/mL and 22623.84 μ g·day/mL respectively following dosing on Day 36.

Clinical Studies

Results from a Phase 2, open label, dose escalation study of bermekimab in participants with moderate-to-severe atopic dermatitis showed that bermekimab appeared to be safe, well tolerated, and active at reducing the severity of atopic dermatitis, including reducing itch and pain (study 2018-PT044, [NCT03496974](#)). Thirty-eight patients across 9 clinical sites in 2 treatment groups received 1 of 2 SC doses: a low (200 mg, n = 10) or high (400 mg, n = 28) dose of bermekimab once weekly for either a 4- or 8-week treatment regimen, respectively. Safety was assessed by pre- and post-treatment measurements of vital signs, clinical laboratory assessments (blood chemistry,

urinalysis, and hematology), allergic reaction monitoring, and adverse event monitoring. Efficacy was assessed by change in Eczema Area and Severity Index (EASI), Investigator Global Assessment (IGA), Numerical Rating Scale, Severity Scoring of Atopic Dermatitis (SCORAD), Patient-Oriented Eczema Measure (POEM), Dermatological Life Quality Index (DLQI), and Global Individual Signs Score from baseline to visit 9. The primary measure of efficacy was the EASI. In the study, 39% of participants in the 400 mg dose group achieved a $\geq 75\%$ improvement in EASI score (EASI-75) after 4 weeks of therapy and 71% achieved EASI-75 at Week 7. An IGA score of 0 (clear) or 1 (minimal) and a ≥ 2 -point decrease from baseline IGA at Week 7 was achieved by 25% of participants in the 400 mg dose group. In addition, 61% of participants in the 400 mg dose group achieved a 4-point or greater improvement in the Pruritus Numerical Rating Scale for overall itch; and 75% achieved a 4-point or greater improvement by Week 8. Furthermore, 80% of participants in the 400 mg dose group achieved a 4-point or greater improvement in the Numerical Rating Scale for pain by Week 8.

Preliminary internal company data from a Phase 2 study, 77474462ADM2002 ([NCT04021862](#)), have recently become available and were used to support decisions about the dose regimens and design of this study. Study 77474462ADM2002 is a double-blind, placebo-controlled study of bermekimab in adult participants with moderate-to-severe AD. The primary endpoint of this study is the percentage of patients achieving EASI-75 at Week 16. Preliminary results from this study are discussed in Section 4.3. Justification for Dose.

In other clinical studies completed to date in AD and HS, bermekimab was well tolerated and demonstrated therapeutic activity. For the most comprehensive clinical information regarding bermekimab, refer to the latest version of the [IB](#) for bermekimab.

2.3. Benefit-Risk Assessment

Based on the available data and the proposed safety measures discussed below, the risks of the dose regimens of bermekimab to be investigated in this protocol appear to be acceptable relative to the potential benefit.

Bermekimab has undergone previous clinical evaluation in diseases such as psoriasis, AD, HS, acne vulgaris, pyoderma gangrenosum (PG), and cancer, as summarized in the latest version of the [IB](#). The collective efficacy and safety results of the Phase 1 and Phase 2 clinical studies in healthy volunteers and patients in dermatologic indications have indicated a favorable benefit-risk profile for bermekimab. In addition, nonclinical evidence suggests that IL-1 α may be an important component for inducing chronic skin inflammation ([Abdel-Razzak 1993](#), [Murphy 2000](#)).

As of 26 February 2020, unblinded data is available from 911 patients treated with JNJ-77474462 in patients with advanced solid tumors, advanced hematologic malignancies, metastatic colorectal cancer, peripheral vascular disease, type II diabetes, acne vulgaris, plaque psoriasis, PG, AD, and HS. To date there has been little evidence of drug-related toxicity, with most adverse events (AEs) appearing to be secondary to worsening of patients' underlying disease states.

An Independent Data Review Committee (DRC) with at least 3 members external to the study team and consisting of a statistician and 2 physicians from clinical science and medical safety will be established to review unblinded safety data at pre-specified timepoints during the study. The DRC may also convene on Ad Hoc basis at the request of the Study Team. The DRC unblinded

safety data review and recommendation will be required for the study to proceed to the higher doses of IV bermekimab in patients with AD. Details will be further described in the DRC Charter. The potential risks for bermekimab in this study are infections, hypersensitivity reactions, and infusion-related reactions.

More detailed information about the known and expected benefits and risks of bermekimab may be found in the IB.

The safety plan for bermekimab includes monitoring of AEs and safety laboratory results, using sites adequately prepared for managing hypersensitivity reactions and patient education for recognizing signs of a serious hypersensitivity reaction such as anaphylaxis.

In addition to the safety laboratory and physical examinations, the Sponsor will implement the additional measures to ensure the safety of the study participants. These additional measures include: 1) a 2-hour, extended infusion time for the first 2 doses to reduce the risk of infusion-related reaction (IRR); 2) a 2-hour post dose observation time for the first 2 doses to ensure tolerability; 3) weekly visits to the investigative site for close monitoring; 4) the establishment of a DRC to review the unblinded safety data at prespecified timepoints in Parts A, B, and C as well as on an ad hoc basis.

Taking into account the measures taken to minimize risk to participants of this study, the potential risks identified in association with bermekimab are justified by the anticipated benefits that may be afforded to participants with moderate-to-severe AD.

2.3.1. Benefit-Risk Assessment for Study Participation

Table 1: Benefit-Risk for Study Participants (Bermekimab)

Potential Risks of Clinical Significance	Summary of Data/ Rationale for Risk	Mitigation Strategy
Risks Due to Study Intervention		
Increased risk of infection.	JNJ-77474462 is a recombinant human IgG1k mAb specific for human IL-1 α . As such, it is considered to be an immunomodulator. Other agents that could be considered in the same pharmacologic class include biologic agents that target IL-1Ra and IL-1 β . Bacterial infections have been reported in clinical trials using JNJ-77474462; however, the infections vary based upon the disease being treated and do not appear to be related to blockade of IL-1 α . No opportunistic infections have been reported.	In this study participants with a history of, or ongoing, chronic or recurrent infectious disease, evidence of active or untreated latent opportunistic infections including TB, will be excluded from the study. As a precaution, participants should be evaluated for TB before administration of study intervention. In addition, participants will be screened for TB prior to study entry and receive regular ongoing evaluation. Participants will be instructed to seek medical attention if they develop signs or symptoms suggestive of an infection, and investigators are instructed in the protocol to monitor for signs or

Table 1: Benefit-Risk for Study Participants (Bermekimab)		
Potential Risks of Clinical Significance	Summary of Data/ Rationale for Risk	Mitigation Strategy
		
symptoms of infections, including TB (Section 8.2.9, Tuberculosis Evaluations).
 
A participant's study intervention must be discontinued if an opportunistic infection including TB develops, and study intervention must be interrupted if the participant develops a serious infection, and continuation or discontinuation of study intervention should be discussed and decided with the Medical Monitor or designee

Infusion-related reactions	
IRR have been reported with the first or second IV infusions of bermekimab. In the largest oncology study, PT023 Version 3, there were reports of infusion reaction in 2.6% (11 of 430) participants compared to 0% in placebo. The majority (n=10) were mild to moderate (Grade 1 to 2) and did not result in discontinuation. There was one Grade 3 infusion reaction, an SAE that resulted in patient discontinuation.
	
In order to mitigate the risk of IRRs, the study drug will be infused over approximately 2 hours for the first 2 doses in the study followed by close monitoring for approximately 2 hours at the investigative site.
 
Availability of resuscitation equipment must be ensured.
 
Any participant who has experienced a Grade 2 IRR, will continue with the 2-hour infusion regimen (and a 2-hour post infusion observation) for the duration of the study.
 
Participants who experience a Grade ≥ 3 IRR should be discontinued from the study.
 
Pre-medication with antihistamines or corticosteroids is not recommended at this time as a lower risk of occurrence for IRR is expected with the approximately 2-hour infusion time. However, based on emerging clinical experience, the sponsor may implement a premedication regimen for all future participants if > 1 incidents of IRR Grade 2 is observed in Part A, or ≥ 1 incidents of IRR Grade 2 is observed in Parts B or C. Such a premedication regimen would be administered approximately 30 minutes before the infusion of the study drug and will consist of an oral non-sedating H1 histamine blocker (eg, loratadine 10 mg orally or

Table 1: Benefit-Risk for Study Participants (Bermekimab)		
Potential Risks of Clinical Significance	Summary of Data/ Rationale for Risk	Mitigation Strategy
Serious hypersensitivity reactions (including anaphylaxis and serum sickness).	Serious hypersensitivity reactions (including anaphylaxis and serum sickness) may occur at any time and not only during administration of bermekimab.	equivalent) and oral paracetamol (eg, acetaminophen 650 mg orally or equivalent). Study intervention must not be administered to individuals with known or suspected intolerance or hypersensitivity to any biologic medication or known allergies or clinically significant reactions to any components of the formulation used in this study.

IgG immunoglobulin G; IL interleukin; IRR infusion related reactions; TB tuberculosis.

More detailed information about the known and expected benefits and risks of bermekimab may be found in the [IB](#).

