6. STUDY INTERVENTION AND CONCOMITANT THERAPY

6.1. Study Intervention Administered

Study intervention administration must be captured in the source documents and the electronic case report form (eCRF).

Bermekimab will be manufactured and provided under the responsibility of the sponsor. Refer to the [IB](#) for a list of excipients.

For details on rescue medications, refer to Section [6.8.4](#), Rescue Medication. For a definition of study intervention overdose, refer to Section [6.7](#), Treatment of Overdose.

Approximately 10 participants are planned to receive weekly 800 mg of IV bermekimab or placebo in Part A. Approximately 30 participants are planned to receive weekly 1200 mg of IV bermekimab or placebo in Part B. After the initial 10 participants (8A:2P) have completed 6 weeks of dosing in Part B, safety, PK, PD, and efficacy will be analyzed to determine an appropriate dose to be used in Part C. Approximately 20 participants are planned to receive the determined dose of bermekimab and placebo. The maximum dose to be considered for Part C will be 2400 mg IV weekly ([Table 2](#)).

Table 2: Description of Interventions

Part Name	Part A	Part B	Part C	N/A
Intervention Name	bermekimab	bermekimab	bermekimab	Placebo
Dose Formulation	sterile liquid formulation of 350 mg (175 mg/mL) of bermekimab in a prefilled syringe (PFS) with an injectable volume of 2.0 mL.	sterile liquid formulation of 350 mg (175 mg/mL) of bermekimab in a PFS with an injectable volume of 2.0 mL.	sterile liquid formulation of 350 mg (175 mg/mL) of bermekimab in PFS with an injectable volume of 2.0 mL.	Saline vials
Unit Dose Strength(s)	175 mg/mL	175 mg/mL	175 mg/mL	N/A
Dosage Level(s)	800 mg intravenous (IV) infusion weekly from Week 0 through Week 15	1200 mg IV infusion weekly from Week 0 through Week 15	TBD mg IV infusion weekly from Week 0 through Week 15	IV infusion weekly from Week 0 through Week 15
Route of Administration	IV infusion	IV Infusion	IV Infusion	IV Infusion
Use	Experimental	Experimental	Experimental	Placebo comparator
Investigational Medicinal Product	Yes	Yes	Yes	No
Non-Investigational Medicinal Product /Auxiliary Medicinal Product	No	No	No	No
Sourcing	Provided centrally by the sponsor			

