6.5. Dose Modification

No treatment or dose adjustment will be permitted throughout the study.

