6.7. Treatment of Overdose

For this study, any dose of bermekimab greater than the highest dose at a single dosing visit within a 24-hour time period will be considered an overdose. The sponsor does not recommend specific treatment for an overdose.

In the event of an overdose, the investigator or treating physician should:

- Contact the Medical Monitor immediately.
- Evaluate the participant to determine, in consultation with the Medical Monitor, whether study intervention should be interrupted or whether the dose should be reduced.
- Closely monitor the participant for AE/SAE and laboratory abnormalities

- Document the quantity of the excess dose as well as the duration of the overdosing in the eCRF.

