7. DISCONTINUATION OF STUDY INTERVENTION AND PARTICIPANT DISCONTINUATION/WITHDRAWAL

7.1. Discontinuation of Study Intervention

A participant's study intervention must be discontinued if:

- The participant withdraws consent to receive study intervention.
- The investigator believes that for safety reasons or tolerability reasons (eg, AE) it is in the best interest of the participant to discontinue study intervention
- Participants who experience a Grade ≥ 3 IRR should be discontinued from the study
- The participant has a serious adverse reaction that is related to an infusion of the study drug administration including a hypersensitivity reaction resulting in bronchospasm, wheezing and/or dyspnea that requires ventilatory support OR that results in symptomatic hypotension with a decrease in systolic blood pressure of 30% from a participant's baseline value or systolic blood pressure <90 mm Hg ([Sampson 2006](#)). In general, discontinuation of study intervention administration must be considered for participants who develop a nonserious but severe infusion-related reaction.
- The participant has a reaction resulting in myalgia and/or arthralgia with fever and/or rash (suggestive of serum sickness and not representative of signs and symptoms of other recognized clinical syndromes) occurring 1 to 14 days after an infusion of study intervention. These may be accompanied by other events including pruritus, facial, hand, or lip edema, dysphagia, urticaria, sore throat, and/or headache.
- The participant becomes pregnant or plans a pregnancy during the study period. Refer to [Section 10.5](#), Appendix 5: Contraceptive and Barrier Guidance.
- The initiation of protocol-prohibited medications, treatments, or interventions (outlined in [Section 6.8](#), Concomitant Therapy) that have an impact on AD efficacy evaluations.
- The participant has a malignancy including squamous cell skin cancer. Consideration may be given to allow participants, who develop ≤ 2 basal cell skin cancers and who are adequately treated with no evidence of residual disease, to continue to receive study intervention.
- A systemic opportunistic infection.
- A recurrent or chronic serious infection.
- The participant is deemed ineligible according to the following TB screening criteria:
 - A diagnosis of active TB is made.

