6.4. Appendix 4 Protocol Deviations

Major protocol deviations will be listed by following category.

- Developed withdrawal criteria but not withdrawn
- Entered but did not satisfy criteria
- Received a disallowed concomitant treatment
- Received wrong treatment or incorrect dose
- Other

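### Section 6.7 offers a dose reduction that 6.5 forbids, and the 7.1 stop list is narrower than Table 1 on opportunistic infection

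*Protocol*

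**What the plan says.** **Overdose.** Section 6.7 asks the investigator or treating physician to determine, with the Medical Monitor, "whether study intervention should be interrupted or whether the dose should be reduced". Section 6.5 states, with no exception, "No treatment or dose adjustment will be permitted throughout the study". Table 2 in section 6.1 gives each part a single dose level. For Part A this is "800 mg intravenous (IV) infusion weekly from Week 0 through Week 15"; Part B has 1200 mg on the same schedule, and Part C has one dose still to be chosen.

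**Opportunistic infection.** The mitigation column of Table 1 (section 2.3.1) requires that "study intervention must be discontinued if an opportunistic infection including TB develops". Section 7.1 introduces its list as mandatory and includes "A systemic opportunistic infection". It also lists several TB stops and recurrent or chronic serious infection. Two of its entries rest on judgement: the sponsor's decision, and the investigator's belief that "for safety reasons or tolerability reasons (eg, AE) it is in the best interest of the participant" to stop.

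**Deviations.** SAP section 6.4 lists major protocol deviations by category. The categories include "Developed withdrawal criteria but not withdrawn" and "Received wrong treatment or incorrect dose".

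**The concern.** Sites act on these sections when something has gone wrong with a participant, so the sections should give one answer.

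On overdose, a site that follows 6.7 can arrive at an action that 6.5 rules out and for which Table 2 supplies no dose. Read literally, 6.5 also sits awkwardly with the interruptions that other sections require or allow.

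On opportunistic infection, 7.1 is the section a site would open to decide whether to stop. It states a narrower mandatory rule than Table 1. A site working from 7.1 alone could keep dosing after a localized, non-TB opportunistic infection.

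The consequence for reporting is small. Whether that participant appears in the SAP's listing of people who met a withdrawal criterion but stayed on treatment depends on which text is taken as the criterion. A dose reduced under 6.7 could be listed as an incorrect dose.

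**Working it through.** Most of this check is a comparison of current operative text. The amendment summary plays no part in it.

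**1. Overdose: 6.7 against 6.5 and Table 2.**
- 6.7 gives two options, interruption or a lower dose.
- 6.5 prohibits dose adjustment for the whole study and makes no exception for overdose. 6.7 does not refer to 6.5.
- Table 2 defines one dose per part and no step-down level.
- A reduced dose therefore cannot satisfy both 6.5 and 6.7. This is a contradiction.
- Interruption is different. Table 1 requires it for serious infection, 6.7 allows it after overdose, and 8.2.9.2 calls for it while close TB contact is investigated. Because 6.5 also bars treatment adjustment, it should say that these interruptions fall outside the ban.

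**2. Opportunistic infection: Table 1 against 7.1.**
- Systemic infection: mandatory stop in both.
- Active TB: mandatory stop in both. 7.1 goes further and also stops for TB symptoms or recent close contact when the participant cannot or will not be evaluated, for a positive or twice-indeterminate QuantiFERON result during evaluation, and for non-compliance with latent TB treatment.
- Localized, non-TB infection that is neither serious and recurrent nor serious and chronic: mandatory stop in Table 1, left to investigator or sponsor judgement in 7.1.
- 7.1 does not say that treatment stops *only* for the listed reasons, so stopping in the third case meets both texts. This is a gap in scope.
- Exclusion criterion 14 in section 5.2 bars anyone who has ever had an opportunistic infection and has no *systemic* limit. Entry and Table 1 agree, and 7.1 is the outlier.

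**3. How many participants could be involved.** The documents give no overdose rate, so only the infection part can be bounded.
- Inputs: Table 1 reports no opportunistic infections, and section 2.3 cites unblinded data on 911 treated patients. That the first statement covers those 911 is an assumption. Planned bermekimab participants from section 9.2: 8 + 24 + 16 = 48.
- Exact one-sided 95% upper bound with 0 events in n: 1 − 0.05^(1/n) = 1 − 0.05^(1/911) = 0.00328, or 0.33% per participant.
- Expected cases at that bound: 48 × 0.00328 = 0.158.
- Chance of at least one at that bound: 1 − (1 − 0.00328)^48 = 0.146, about 15%.

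These figures cover all opportunistic infections, including the systemic and TB cases that both texts already stop.

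**The case against.** The strongest reply is that neither mismatch could do much.

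On infection, Table 1 and 7.1 add to each other, so a reader of both already has the stricter rule. The protocol does not define opportunistic infection. Its only named examples, in exclusion criterion 14, are cytomegalovirus, pneumocystis and aspergillosis, while mucocutaneous candidiasis is placed under chronic or recurrent infection in criterion 5. The gap may therefore be nearly empty. Table 1's hold for serious infection and the judgement-based entries in 7.1 are further backstops. Adding *systemic* to Table 1, or defining the term, would also align the texts.

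On overdose, 6.7 requires consultation with the Medical Monitor. The investigator is blinded, doses are prepared by unblinded staff under the IWRS assignment (6.3), and departures from protocol call for contact with the sponsor (10.3.1).

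Most of this stands, and it limits the point. A reader might infer that Table 1 and 7.1 contradict each other, or that 7.1 tells sites to continue dosing. The text does not support either reading. A reader might also infer that a site could lower a dose on its own; the Medical Monitor step argues against that. What the reply does not remove is that 6.7 still offers an option that 6.5 forbids, and that 7.1 still omits a stop that Table 1 makes mandatory.

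**Conclusion.** Both inconsistencies are present in the current protocol. The 6.5 and 6.7 mismatch is a direct contradiction. The Table 1 and 7.1 mismatch is a difference in scope.

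Severity is minor. At the upper bound, about 0.16 opportunistic infections of any kind would be expected among 48 planned bermekimab participants. It is tempting to take the 15% as the chance of a case falling in the gap. It is not: the localized non-TB subset is smaller, and its size cannot be estimated from the documents. The bound also assumes that the zero count applies to all 911 patients. It carries over from other diseases and lower doses with unmatched exposure time, so it may not hold exactly here.

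Nothing supports a claim that trial validity is affected. No efficacy or safety analysis changes; only the classification of a major deviation might. The sponsor ended the study early with few participants enrolled, and SAP sections 1 and 6.2 plan listings only, which reduces the practical effect further. The reason to act is that the safety instructions should agree and the repair costs almost nothing.

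**What to change.** - **6.7:** delete the clause on reducing the dose and leave interruption as the option to decide with the Medical Monitor.
- **6.5:** add one sentence saying that safety interruptions required or allowed elsewhere (Table 1 for serious infection, 6.7 for overdose, 8.2.9.2 for close TB contact) are not dose adjustments and are permitted.
- **7.1:** delete *systemic* so that the entry matches Table 1. This direction is preferred to narrowing Table 1 because exclusion criterion 14 also has no such limit. The small downside is a mandatory stop for an occasional mild, localized case.
- **Optional:** cross-reference Table 1's serious-infection hold in 5.5, which now covers only COVID-19, and in 7.1. The hold already applies, so this is tidying.

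The cost is one deleted word, one deleted clause and one added sentence, plus two cross-references if wanted. There are no new procedures, visits or participants, and the SAP does not change.
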